2. OBJECTIVES

The primary objective of the study is to identify risk factors for cancer onset in the population affected by T2D.

Secondary objectives include:

1. Description of demographic, clinical, and first-line therapy characteristics of patients at the diagnosis of T2D.
2. Evaluation of risk factors for recurrence, presence of a second cancer unrelated to the first, and presence of both events in patients who have had cancer.
3. Investigating the correlation between patient characteristics and time to cancer onset.

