3.8 Sample Size

Assuming a type I error of 0.05, a power of 80%, a prevalence of subjects with high glycated hemoglobin levels of 13%, and a correlation between covariates in the model of 0.1, it will be necessary to identify 779 cancer cases to highlight a Hazard ratio of 1.2 for the association between glycated hemoglobin and cancer onset.

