3.9 Statistical Analysis

Descriptive statistics will be calculated to summarize patient information.

Categorical variables will be reported as absolute frequencies and percentages, while numerical variables will be reported as mean and standard deviation or median (Q1-Q3) if not distributed according to a normal random variable according to the Shapiro-Wilk test and observation of the QQ plot.

SCDU di Endocrinologia

AOU Maggiore della Carità, [name]
[contact] (Reparto); [contact]
[contact]

Univariate and multivariate Cox proportional hazards regression models will be used to estimate hazard ratios (HRs) and corresponding 95% confidence intervals (95% CI) for the association between some risk factors, including particularly glycemic level, and cancer onset. The stepwise method will be used to select variables to include in the model. For this analysis, time to event will be calculated as the number of years between cancer onset and diabetes diagnosis for subjects who develop the cancer, and as the number of years between the last available visit and the date of diabetes diagnosis. The possibility of conducting an analysis separately for cancer type or considering specific cancer types based on the number of observed events will be evaluated. The same models will be used to estimate the association with the risk of recurrence, second cancer, or both in patients who have developed cancer. In this case, time to event will be calculated considering the difference in years between recurrence onset, second cancer, or last visit and the onset of the first cancer.

Linear regression models will be used to evaluate the relationship between variables measured at diagnosis and time to cancer onset. In case the assumptions of the linear model are not met (normality of residuals and homoscedasticity), the Spearman correlation coefficient will be calculated to measure the correlation between numerical variables and time to tumor onset, while the Mann-Whitney or Kruskall-Wallis tests will be used when variables measured at baseline are categorical.

The significance level will be set at 0.05, and all tests performed will be two-tailed. Finally, the analyses will be conducted using SAS software (version 9.4; SAS Institute, Cary, NC, USA).

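### The adjusted hazard ratios that answer the primary objective come from a stepwise-selected Cox model with ordinary 95% intervals, and nothing allows for the selection or for the roughly 20 candidates

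*Combined protocol and SAP*

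**What the plan says.** Section 2 sets the aim: "The primary objective of the study is to identify risk factors for cancer onset in the population affected by T2D". Section 3.9 answers it with univariate and multivariate Cox models that give HRs and 95% intervals "for the association between some risk factors, including particularly glycemic level, and cancer onset". On how the multivariate model is built there is one sentence: "The stepwise method will be used to select variables to include in the model". On error control there is also one: "The significance level will be set at 0.05, and all tests performed will be two-tailed".

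The plan gives no entry or stay level, no candidate list and no variables to be kept regardless of the data. It describes no multiplicity adjustment, bootstrap, shrinkage or interval that allows for selection. Glycemic level is singled out but is not said to be forced into the model. Section 3.8 justifies a sample size for HbA1c only. The candidates have to be inferred from the extraction list in section 3.7.

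**The concern.** An ordinary 95% interval has its stated coverage when the model is fixed before the data are seen. Here the data decide which factors appear in the adjusted model, and a factor is more likely to appear when chance has pushed its estimate away from 1. The intervals then shown are too optimistic as a set, and weak effects look stronger than they are.

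A second, separate problem is that many candidates are tested at 0.05 with no correction, so some listed risk factors may be chance findings. Section 4 says the results are to inform prevention, so both problems bear on how the main table will be used.

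**Working it through.** **Inputs.** Events: 779 (section 3.8). Correlation: "a correlation between covariates in the model of 0.1" (section 3.8). Level: 0.05 two-sided (section 3.9). Candidates: counted from section 3.7. The true effects and the number of null candidates are assumptions.

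**The plan's own figure.** The standard Cox events formula is D = (z_α/2 + z_power)² / [p(1−p)(ln HR)²(1−R²)]. With p = 0.13 and HR 1.2, D = 7.849 / (0.1131 × 0.03324) = 2088 for R² = 0, 2109 for R² = 0.01 and 2320 for R² = 0.10. It does not return 779. A close match (780.1) appears only if the SD, 0.336, replaces the variance and 0.1 is used as R². That is a separate issue. Below, 779 is taken as the planned number of events.

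**Candidates at T0.** Single coefficients: sex, age, smoking, alcohol, weight, HbA1c, creatinine clearance, ALT, AST, LDL-c, TG and family history (12), plus six complications (6). BMI in three classes adds 2 and treatment in nine classes adds 8. That is 20 variables and 12 + 6 + 2 + 8 = 28 coefficients. Average fasting glucose makes 21 variables. Counting T0, T1 and average values separately gives about 31.

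**Coverage of retained intervals, by hand.** Suppose 15 candidates are null and 5 are strong enough always to be kept with 95% coverage.
- Stay level 0.05: 15 × 0.05 = 0.75 null factors are kept on average, and none of their intervals covers 1. Coverage = (5 × 0.95) / (5 + 0.75) = 4.75 / 5.75 = 83%.
- Stay level 0.15: 15 × 0.15 = 2.25 null factors are kept. Of these, 0.10/0.15 = two thirds (1.5) have intervals that cover 1. Coverage = (4.75 + 1.5) / 7.25 = 86%.

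**Coverage by simulation.** Setting: large-sample normal approximation to the Cox score, 20 single-coefficient candidates, 779 events, r = 0.1, 10-15 null, assumed true HRs of 1.05-1.20 per SD, forward entry with backward removal.

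| | Stepwise, 0.05 | Stepwise, 0.15 | Full model, no selection |
|---|---|---|---|
| Coverage of reported intervals | 78-88% | 84-90% | 95% |
| Reported intervals excluding 1 | 100% | 68-78% | not fixed by selection |
| At least one null factor kept, or p < 0.05 in the full model | 43-51% | 78-91% | 40-54% |

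**Multiplicity alone.** 1 − 0.95¹⁰ = 40% and 1 − 0.95¹⁵ = 54%. These match the full-model range, so at 0.05 the false-factor risk comes from the number of tests and hardly at all from stepwise. If all 20 candidates were null it would be 1 − 0.95²⁰ = 64%. At 0.15, 1 − 0.85¹⁰ = 80% and 1 − 0.85¹⁵ = 91%.

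**Overstatement when kept (0.05).** For HR 1.05 per SD, the expected z is ln 1.05 × √779 = 0.0488 × 27.9 = 1.36. The chance of exceeding 1.96 is 0.275. The mean z given that it does is 1.36 + φ(0.60)/0.275 = 1.36 + 1.21 = 2.58, which corresponds to exp(2.58/27.9) = 1.10. For HR 1.20 per SD the expected z is 0.1823 × 27.9 = 5.09, so the factor is almost always kept and is little distorted.

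**The plan's own HbA1c effect.** HR 1.2 for a factor present in 13% is exp(0.1823 × 0.336) = 1.06 per SD, so it belongs with the weak effects. With 19 null companions and selection at 0.05, simulation keeps it in about 40% of runs and reports it at about 1.34 when kept. This applies only if HbA1c is not forced in.

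**The case against.** A reader might infer that every interval the study reports must exclude 1. The documents do not support that:
- No stay level is stated. The 0.05 in section 3.9 is a general level for tests. Reading it as the stay level is natural but is not written down, and at 0.15 only 68-78% of retained intervals exclude 1.
- A factor with several classes, such as treatment or BMI, can be kept on a joint test while single-class intervals include 1.
- A variable forced into the model need not have an interval that excludes 1.
- The univariate HRs are also reported and are not selected by stepwise, though they are unadjusted and face the same uncorrected multiplicity.

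A reader might also blame stepwise selection for the 40-55% chance of a false risk factor. At 0.05 the full model has nearly the same risk, so removing stepwise would not cure it.

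The coverage figures are also open to challenge, because they depend on effects that the documents do not give. When the assumed true HR was varied from 1.05 to 1.3 per SD, coverage at the 0.05 level ran from 56% to 92%. For true factors of at least 1.1 per SD it was about 95%. This stands, and it is why a range is given. The shortfall is nevertheless present across that range.

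Finally, section 3.9 speaks only of some risk factors and section 3.7 collects data when possible, so the count of 20 is an inference. It could be argued that the study is exploratory, but the plan does not say so.

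**Conclusion.** The point holds in this form. The adjusted intervals offered in answer to the primary objective ignore the selection that produced them. Under either reading of the stay level they fall short of 95%: about 78-88% at 0.05 and 84-90% at 0.15, given 779 events, r = 0.1, 10-15 null candidates out of 20 and true HRs of 1.05-1.20 per SD. Weak effects are exaggerated when kept, and effects near 1.2 per SD are not materially changed. Exclusion of 1 by construction is true only for retained single-coefficient factors, and only if the stay level is 0.05 or stricter.

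The risk of at least one chance risk factor, about 40-55%, is a multiplicity problem that exists with or without stepwise. A looser stay level raises it to about 78-91%. The plan should be changed on both counts.

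**What to change.** In section 3.9, replace stepwise selection for the main result with one prespecified multivariable Cox model of the T0 candidates, and report every HR with its 95% interval. List the candidates. Choose in advance between overlapping variables (weight or BMI, for example) and merge overlapping treatment classes: the basal bolus class on its own is contained in the basal bolus class with optional additions.

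At 779 events and about 28 coefficients this gives 779/28 = 27.8 events per coefficient, and more once overlaps are removed. The documents give no cohort size or expected event count, and some values will be missing. State, therefore, that if fewer events are available the list will be shortened without reference to the outcome.

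Report factors other than HbA1c as hypothesis-generating, with false-discovery-rate-adjusted p-values. This is the step that addresses false risk factors. If a stepwise model is kept, show it as secondary, state its entry and stay levels, and give bootstrap selection frequencies from re-running the whole selection.

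The cost is revised wording, modest extra computing, somewhat wider intervals and a longer table. No new data are needed.

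### Stepwise Cox selection is carried over to recurrence and second cancer, where events are fewer and unplanned for, so retained hazard ratios are likely to be overstated and the selected factors unreliable

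*Combined protocol and SAP*

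**What the plan says.** For the subset with a first cancer, section 2 (secondary objective 2) calls for "Evaluation of risk factors for recurrence, presence of a second cancer unrelated to the first, and presence of both events".

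Section 3.9 plans univariate and multivariate Cox models for cancer onset and states: "The stepwise method will be used to select variables to include in the model". It then adds, for patients with a first cancer: "The same models will be used to estimate the association with the risk of recurrence, second cancer, or both". On testing it says only: "The significance level will be set at 0.05, and all tests performed will be two-tailed".

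For these outcomes the document gives no candidate list, entry or stay threshold, limit on parameters, shrinkage, validation, multiplicity control or exploratory label. Section 3.9 makes analyses by cancer type depend on how many events are seen, but sets no such condition here. Section 3.8 sizes the onset analysis only: 779 cancer cases for an HR of 1.2.

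**The concern.** Stepwise selection keeps a factor only when its estimate clears a significance threshold. With few events that threshold lies far from HR 1, so a modest real effect is usually missed, and when it is kept its estimate is too large. The first recurrence or second cancer can occur only in a patient with a first cancer. Such events would therefore match the onset events in number only if every patient had one, and having both is rarer still.

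The possible factors are many. Section 3.7 lists about 23 variables at one time point and about 31-32 counting both visits. Diabetes treatment alone has nine classes.

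Section 4 intends the findings to inform prevention. A list of recurrence factors that mixes chance findings with exaggerated real ones would mislead that use.

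**Working it through.** **Plan's own figure.** Inputs from section 3.8: "Assuming a type I error of 0.05, a power of 80"%, "a prevalence of subjects with high glycated hemoglobin levels of 13"%, "a correlation between covariates in the model of 0.1", HR 1.2, 779 cases. The usual Cox formula is D = (1.960 + 0.842)² / [p(1−p)(ln HR)²(1−R²)].

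- p(1−p) = 0.13 × 0.87 = 0.1131; ln 1.2 = 0.1823, squared 0.03324.
- R² = 0: D = 7.849 / (0.1131 × 0.03324) = 2,088. R² = 0.01: 2,109. R² = 0.1: 2,320.

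The 779 is therefore not reproduced. The nearest match, 780, comes from using √0.1131 = 0.336 in place of 0.1131 with R² = 0.1. That is a separate point. Here 779 serves only as the plan's number of first cancers.

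**Assumed events.** The document gives no figure. Taking 10%, 20% and 30% of 779 gives 78, 156 and 234.

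**Smallest estimate that can be retained.** For a factor with prevalence p, SE(ln HR) ≈ 1/√[D p(1−p)], so the estimate must reach HR = exp{1.96/√[D × 0.1131]}, or its reciprocal if protective. This takes 0.05 as the threshold and ignores correlation with other covariates.

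| Events D | 1.96 × SE | Minimum HR | Ratio to ln 1.2 | Power at HR 1.2 |
|---|---|---|---|---|
| 78 | 0.660 | 1.93 | 3.6 | 8% |
| 156 | 0.467 | 1.59 | 2.6 | 12% |
| 234 | 0.381 | 1.46 | 2.1 | 16% |

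A factor with a true HR of 1.2 and 13% prevalence, kept in the right direction, would thus be overstated at least 2.1-fold on the log scale at 234 events and 3.6-fold at 78 under this approximation.

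**Simulated stepwise Cox selection.** Assumed: 779 patients, 25 mildly correlated binary candidates, 0.05 to enter and to stay, 300 runs per setting. Each cell gives the share of selected factors that are false, then the inflation of the log HR for real factors that were kept.

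| Real factors | 78 events | 156 events | 234 events |
|---|---|---|---|
| 5 at HR 1.2, prevalence 30% | 57%, 3.2× | 50%, 2.35× | 43%, 2.0× |
| 5 at HR 1.2, prevalence 13% | 61%, 3.4× | 59%, 2.7× | 49%, 2.4× |
| 5 at HR 1.5, prevalence 30% | 30%, 1.6× | 23%, 1.2× | 20%, 1.1× |
| 10 at HR 1.5, prevalence 30% | 17%, 1.6× | 10%, 1.25× | 9%, 1.1× |

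HR 1.5 was simulated at 30% prevalence only. For 13% prevalence a simpler normal approximation gives power of 23% at 78 events and 55% at 234. With 20 null and 5 real factors, the false share is 1.0/(1.0 + 5 × 0.23) = 47% and 1.0/(1.0 + 5 × 0.55) = 27%, with inflation of 2.1× and 1.3×.

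**What the event count changes.** With 20 null candidates, 20 × 0.05 = 1 false factor is expected per model. The simulations with 5 real factors gave 0.82 to 1.07 at 78-234 events, and 0.93 (prevalence 30%) and 1.23 (13%) at 779 events with HR 1.2 (40 runs). The number of false factors is essentially unaffected. At HR 1.2 and 30% prevalence, the real factors found out of five were 0.72, 1.01 and 1.43 at 78, 156 and 234 events, against 3.65 at 779. At 779 events the false share was 20% and the inflation 1.2× (33% and 1.5× at 13% prevalence).

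**The case against.** The strongest objection is that the numbers come from assumptions. The plan does not state the event fraction, the candidates, how many of them matter, how strongly, or the stepwise threshold. A reader might infer that about half of the reported factors will be false and the real ones about doubled. The document does not support that as a firm statement: it holds if true HRs are near 1.2 and about one candidate in five is real, and it fades as true effects grow. In the normal approximation for HR 2.0 at 13% prevalence, the inflation is 1.36-fold at 78 events and 1.03-fold at 234.

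A reader might also infer that few events create more false factors. They do not. The expected number is about 0.05 per null candidate at any event count. Few events reduce the real factors found, which raises the false share, and inflate those kept.

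Nor does section 3.7 fix a candidate set. It is an extraction list, to be filled where data allow, and section 3.9 speaks only of some risk factors. Entering 31 variables means using weight with BMI and both visits' values, yet that count leaves out cancer treatment and cancer type, which are natural candidates for recurrence. A fixed ratio of events to candidates therefore cannot be claimed.

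Finally, reusing the models could mean Cox regression in general, or the variables already selected for onset, rather than a fresh selection. The sentence allows this. If the onset variables were carried over unchanged, the retention filter would not act on these outcomes, although power would still be low. The plan needs to say which is meant.

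What remains after these points is a selection method carried to a smaller event set without sizing or safeguard.

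**Conclusion.** The concern holds in conditional form, for a secondary objective. Read as stepwise selection repeated for recurrence, second cancer or both, the plan would tend to report overstated HRs and an unstable set of factors. The retention threshold depends on few assumptions: with 78-234 events, a factor at 13% prevalence needs an estimated HR of about 1.9 to 1.46. The false share and inflation depend on much more: 43-61% and 2.0-3.4-fold with 5 of 25 candidates real at HR 1.2, and 9-30% and 1.1-1.6-fold with 5 or 10 of 25 real at HR 1.5 and 30% prevalence. They illustrate a range and do not predict this study's result.

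**What to change.** In section 3.9, replace stepwise selection for these outcomes with one of the following:

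- A short Cox model specified in advance, with the number of parameters limited by the observed events. Enter cancer type in a few collapsed groups and consider cancer treatment among the covariates. Do not stratify on all 13 cancer-type groups of section 3.7: 78-234 events would average 6 to 18 per stratum (78/13 and 234/13), and the gynecological and male genital strata would carry no information on sex.
- If more factors must be examined, a ridge- or LASSO-penalised Cox model with bootstrap selection frequencies. LASSO selection can itself be unstable at these event counts, so the frequencies should be reported with the estimates.

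State the expected number of each event with its assumptions, list the candidates, say whether any variable set is carried over from the onset model, and report the results as exploratory.

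The cost is revised SAP wording and a different model call, with no new data. The downside is that fewer factors are examined, or that the estimates are shrunken.

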Finally, regarding cancer, treatment will be categorized into three classes: chemotherapy, surgery, and radiotherapy. Additionally, cancer types will be divided to ensure greater homogeneity among groups, including the nervous system, head and neck, thorax, gastrointestinal, gynecological, urinary tract, male genital system, skin, blood, breast, soft tissues, endocrine glands, and neuroendocrine cancers.

Such information will be collected at the diabetes diagnosis visit and the last visit before cancer onset for subjects experiencing the event, and at the last available visit for the remaining subjects.

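### The recurrence and second-cancer models do not commit to stratifying or adjusting for first-cancer type, and the event time for 'both' is undefined

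*Combined protocol and SAP*

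**What the plan says.** Section 2 (Objectives), secondary objective 2, asks for risk factors for recurrence, for an unrelated second cancer, and for the "presence of both events in patients who have had cancer".

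Section 3.9 specifies univariate and multivariate Cox models with stepwise selection for cancer onset. It then states: "The same models will be used to estimate the association with the risk of recurrence, second cancer, or both", in patients who have developed cancer. Time is "the difference in years between recurrence onset, second cancer, or last visit and the onset of the first cancer".

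Section 3.7 states that "cancer types will be divided to ensure greater homogeneity among groups" and lists 13 groups, among them gynecological, male genital system, breast, blood and skin. Section 3.9 names no strata and no forced covariates. It refers to cancer type once, just before the recurrence sentence and within the onset analysis: whether to analyse types separately, or particular types, is to be considered in the light of event numbers.

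**The concern.** The 13 groups are likely to have very different recurrence rates. If a candidate factor is also distributed unequally across them, a Cox model with one baseline hazard for all types credits the factor with part of the difference between tumour types. A factor with no effect within any type can then be reported as a risk factor for recurrence. Section 4 intends the findings to guide prevention strategies, so such a result would mislead.

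There is a second, independent problem. Section 2 lists having both events as its own outcome. The time rule in section 3.9 names the recurrence, the second cancer and the last visit. It does not say which date applies to a patient with both events, or how a patient with only one of them is handled in that model. Two analysts could build different datasets from the same text.

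**Working it through.** **Plan's own figures.** The documents give no event count, effect size or power for these models. The only figure is 779 cancer cases for the onset model (section 3.8). Putting the stated inputs into the usual Cox events formula, D = (z₀.₉₇₅ + z₀.₈₀)² / [p(1−p)(ln HR)²(1−ρ²)], gives 7.849 / (0.13 × 0.87 × 0.03324 × 0.99) ≈ 2,109, not 779. That mismatch is a separate matter. Here 779 serves only as a convenient number of first-cancer patients.

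**What links a factor to type.** Gender is a collected variable (section 3.7), and the gynecological and male genital groups are sex-specific, so gender is associated with type by construction. The documents give no HbA1c, BMI or smoking profile by type, and no recurrence rate by type. Everything below on size is therefore assumed.

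**Mechanism by hand.** Take two equal type groups, A and B, exposure 10% in A and 16% in B, and no effect within either.
- Share of exposed patients in B: 0.16 / (0.10 + 0.16) = 0.615.
- Share of unexposed patients in B: 0.84 / (0.90 + 0.84) = 0.483.
- With annual recurrence hazards of 2% in A and 10% in B, the average starting hazard is 0.385 × 0.02 + 0.615 × 0.10 = 0.0692 in the exposed and 0.517 × 0.02 + 0.483 × 0.10 = 0.0586 in the unexposed.
- Apparent hazard ratio: 0.0692 / 0.0586 = 1.18, although the true value is 1.0.

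**Simulation.** 779 patients, exponential recurrence times, uniform censoring between 1 and 10 years, 1,000 replicates per scenario, two-sided 0.05 tests, true hazard ratio 1.0, exposure 10% versus 16%:

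| Annual hazards A/B | By hand at time 0 | Pooled HR | Pooled false positives | Stratified by type |
|---|---|---|---|---|
| 2% / 5% | 1.12 | 1.10 | 8% | about 1.00, 5% |
| 2% / 10% | 1.18 | 1.19 | 14% | about 1.00, 5% |
| 2% / 15% | 1.21 | 1.22 | 24% | about 1.00, 5% |

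A 2,000-replicate run of the middle scenario gave 16%, which is within simulation error.

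**Sensitivity to the assumptions.**
- Exposure equal in both groups: no bias under the null (hazard ratio about 1.00, 5% rejection).
- Exposure 12% versus 14%: hazard ratio about 1.06, 6.5% rejection.
- Exposure 8% versus 18%, lower hazard 3% a year, censoring uniform over 0 to 16 years: 1.15 and 13% for a two-fold hazard difference, 1.29 and 37% for a four-fold difference.
- A factor tied more strongly to type, as gender might be (30% versus 70%): 1.42 and 50% at hazards 2%/5%; 1.78 and 97% at 2%/10%. The stratified results stay at 1.00 and about 5%.
- Equal exposure but a true hazard ratio of 1.5 (hazards 2%/15%): pooled estimate 1.38 to 1.39 with power 47% to 50%; stratified 1.50 with 64% to 65%.

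Second cancer was not simulated. The same reasoning applies to it only if second-cancer rates differ by first-cancer type.

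**'Both'.** Setting section 2 beside section 3.9 leaves two readings. If the outcome is having had both events, it is complete only at the later date, which the time rule does not name. If the phrase means a composite of either event, timing at the first event is valid, but section 2 lists both events as a separate outcome and section 3.9 does not call it a composite.

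**The case against.** *The plan does contemplate type.* The sentence before the recurrence models raises type-specific analysis, and a reader could carry it forward. It is conditional, however, and attached to the onset analysis. Separate models by type are also least feasible here, because these outcomes arise only among the cancer cases. What stands is that one may not infer from the silence that type will never be used.

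*Stepwise selection could admit type.* Type is recorded, and no candidate list excludes it. When type was added as an ordinary covariate in the simulated scenarios, it was significant in every replicate, and the adjusted results matched the stratified ones (hazard ratio 0.98 to 1.00, 4% to 5% rejection in the null scenarios). This stands: adjustment would serve as well as stratification. But type is not named as a candidate, many groups with few events each are harder to retain than two large ones, and the univariate models stay exposed.

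*Type may be a mediator.* Section 3.7 collects the factors at diabetes diagnosis and before cancer onset. A factor that influences which tumour arises may act on recurrence partly through type, and the within-type hazard ratio then answers a different question from the overall association. This stands. A reader might infer that type is purely a confounder and that only the stratified estimate is valid; the documents do not settle that.

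*A reader might infer that 'both' is timed at the earlier event, so that patients are classified by something yet to happen.* Section 3.9 never says so. Only the charge that the time is undefined is supported.

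**Conclusion.** The point holds in a limited form and should be acted on. Section 3.9 does not commit the recurrence and second-cancer models to any use of first-cancer type. The univariate models, and any stepwise model that omits type, can therefore present tumour-type differences as risk factors. The size cannot be computed from the documents. It depends on an assumed link between factor and type and on assumed differences in recurrence rate, and it vanishes under the null when exposure is equal across types. A reader might infer that the HbA1c, BMI or smoking results will be biased by the amounts shown; the documents support a link with type for gender only.

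The undefined time for 'both' is a real gap but a separate one: it does not cause type differences to appear as risk factors.

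**What to change.** Add to section 3.9: *All recurrence and second-cancer models, univariate and multivariate, are stratified by first-cancer group (or include it as a forced covariate), merging groups with few events. Hazard ratios are interpreted as within-type associations. An unstratified model may be shown as a sensitivity analysis. The outcomes are (a) time to recurrence, (b) time to second cancer and (c) time to the first of either. Patients with both events are described only, or are timed at the later date.* Align secondary objective 2 in section 2 with these outcomes.

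The cost is one STRATA statement on a variable already collected, plus these sentences. Strata with no events, or with no variation in a factor (gender in the sex-specific groups), contribute no information, and effects that act through tumour type are not captured; the unstratified sensitivity model partly addresses the latter.
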